5.2.2. Progression-free Survival (PFS)

Progression-free survival is defined as the time from the date of seribantumab treatment initiation (Dose 1) to the first documented radiographical progression of disease using RECIST v1.1, or death from any cause, whichever comes first.

PFS in days will be calculated as:

• PFS (days) = Date of PD or death (whichever is earlier) or Date of censoring – first dose date + 1

PFS in months will be calculated as:

• PFS (months) = 12*PFS (days)/365.25

The following table summarizes the PFS censoring rules:

Table 1:Progression Free Survival		Survival Censoring Rules	
		Primary analysis	Sens

	Primary analysis	Sensitivity analysis		
	(Censoring rules)	(Censoring rules)		
No PD, no death, no NACT initiated	Censored at last tumor assessment. If no evaluable tumor assessment, censored on the first dose date.	Censored at last tumor assessment. If no evaluable tumor assessment, censored on the first dose date.		
No PD, no death, NACT initiated	Censored at the last tumor assessment prior to NACT. If no evaluable tumor assessment, censored on the first dose date.	Censored at last tumor assessment regardless of NACT. If no evaluable tumor assessment, censored on the first dose date.		
PD or death, no NACT initiated	PFS event at the date of PD or death	PFS event at the date of PD or death		
PD or death prior to or on date NCAT initiated if patient received the NACT	PFS event at the date of PD or death	PFS event at the date of PD or death		
PD or death after NACT	Censored at the last tumor assessment prior to NACT	PFS event at the date of PD or death		
PD or death after 1 missed tumor assessment	PFS event at the date of PD or death	PFS event at the date of PD or death		
PD or death after 2 or more missed tumor assessment	Censored at last tumor assessment prior to PD or death	PFS event at the date of PD or death		
Abbreviations: PD = progressive disease; PFS = progression-free survival; NACT = new anticancer therapy				

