	
(Section 5.2.4.3) to manage treatment related toxicities are permitted during weekly dosing. After 12 months of weekly dosing, patients who have tumor response (CR or PR) per RECIST v1.1 may transition from treatment with seribantumab 3,000 mg once every week to once every 2 weeks (Q2W) after discussion with and approval from the Sponsor.
 
Note: Previous dosing regimens for patients enrolled under prior protocol versions are described in detail in Appendix A.
 
Patients are expected to be treated until investigator-assessed progressive disease or unacceptable toxicity. Treatment beyond progression is permitted if the Investigator determines that the patient may derive clinical benefit from continued exposure to seribantumab. Tumor assessments will be measured and recorded by the local radiologist beginning at weeks 6, 12, 18 and 24 with a \pm 2-week window and subsequently every 8 weeks (\pm 2 weeks) through Week 48, followed by every 12 weeks (\pm 2 weeks) beginning at Week 60 until disease progression and evaluated using the RECIST guidelines (version 1.1). Patients that discontinue study treatment for reasons other than disease progression including due to toxicities will continue to receive tumor assessments as outlined above until initiation of next anti-cancer therapy, clinical disease progression, death, or withdrawal of consent. In addition, an independent central review of scans will be conducted. All images will be submitted to a central imaging facility for this purpose and will be assessed by independent reviewers in accordance with the Imaging Charter. After patients discontinue seribantumab treatment, survival information and information about subsequent therapies will be collected until death or study closure, whichever occurs first. An optional biopsy may be obtained at the time of progression to explore mechanisms of seribantumab resistance.

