7.7. Disease Evaluation

Tumor response will be evaluated by the local radiologist according to the RECIST v1.1 (Eisenhauer et al., 2009) to establish disease progression by computerized tomography (CT) or magnetic resonance imaging (MRI) of chest, abdomen, and pelvis at minimum, and in additional regions such as head, neck, or extremities, as appropriate if disease or symptoms are present. Patients enrolled with a history of central nervous system (CNS) metastases should additionally have a head CT/MRI scan with contrast performed at each tumor assessment. The same method of assessment must be used throughout the study. Please refer to image acquisition guidelines for the requirements for image collection and scanner qualification. Independent retrospective central reviews of all scans may be conducted in addition to review performed by the local radiologist. Investigators should choose target and non-target lesions in accordance with RECIST v1.1 guidelines. Follow-up measurements and overall response should also be in accordance with these guidelines. To be assigned a status of confirmed PR or CR, changes in tumor measurements must be confirmed by repeated assessments that should be performed ≥ 28 days after the criteria for response are first met.

Patients that discontinue study drug administration for reasons other than progressive disease including due to toxicities will continue to receive tumor assessments beginning at weeks 6, 12, 18 and 24 with a ± 2 -week window and subsequently every 8 weeks (± 2 weeks) through Week 48, followed by every 12 weeks (± 2 weeks) beginning at Week 60 until disease progression and evaluated using the RECIST guidelines (version 1.1). Patients will be evaluated until disease progression, initiation of next anti-cancer therapy, death, or withdrawal of consent.

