5.2. Secondary Efficacy Endpoints

5.2.1. Duration of Response (DoR)

Duration of response is defined as the time from the start date of CR or PR (whichever response status is observed first and subsequently confirmed), to the date of first documented radiographical progression of disease using RECIST v1.1, or death from any cause, whichever comes first. DoR will be calculated for patients who are responders, i.e., those who achieve a confirmed CR or PR.

DoR in days will be calculated as:

• DoR (days) = Date of PD or death (whichever is earlier) or Date of censoring – first date of PR/CR + 1

DoR in months will be calculated as:

• DoR (months) = 12*DoR (days)/365.25

DOR will follow the same censoring rules as PFS primary analysis in Table 1 in section 5.2.2.

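### No planned PFS analysis counts new anticancer therapy or clinical progression as an event, so the sensitivity analysis is a weak check; the SAP's DoR censoring also departs, unlisted, from the protocol

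*SAP*

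**What the plan says.** - **PFS event.** SAP 5.2.2 measures PFS from first dose "to the first documented radiographical progression of disease using RECIST v1.1, or death from any cause, whichever comes first". Clinical progression and the start of NACT are not events.
- **When scans stop.** The protocol synopsis and Protocol 3.1 continue scans, for patients who stop treatment for reasons other than progression, "until initiation of next anti-cancer therapy, clinical disease progression, death, or withdrawal of consent". Protocol 7.7 words the stop differently: "Patients will be evaluated until disease progression, initiation of next anti-cancer therapy, death, or withdrawal of consent", with no mention of clinical progression.
- **End-of-treatment (EOT) scan.** Protocol Table 4 (footnote 12) and SAP 3.6 require a scan at the EOT visit for everyone who stops for a reason other than progression. Protocol 5.4 and 6.5 place that visit within 4 weeks of the last dose and before any later anticancer therapy.
- **SAP Table 1, NACT.** In the primary column, a patient who starts NACT without progression is censored at the last scan before it, and later progression or death is disregarded. In the sensitivity column, later progression or death counts. A patient with neither is "Censored at last tumor assessment regardless of NACT".
- **SAP Table 1, missed scans.** The row "PD or death, no NACT initiated" is an event in both columns. The row "PD or death after 2 or more missed tumor assessment" is censored in the primary column and an event in the sensitivity column.
- **DoR.** SAP 5.2.1 states: "DOR will follow the same censoring rules as PFS primary analysis in Table 1". Protocol 10.5.2 and the synopsis say that NACT closes the response, and 10.5.2 reserves censoring for responders with no progression, death or NACT.

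**The concern.** Kaplan-Meier estimation assumes that censored patients have the same prospects as those still followed. A patient who deteriorates and moves to another therapy without radiographic progression breaks that assumption: the curve treats the patient as progression-free at the last scan and then drops the patient from the risk set. PFS and DoR then read too long. The trial is single-arm, so no comparison group shares the bias, and SAP 6.3 and 8 now rest all efficacy on investigator assessment in an open-label study.

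A sensitivity analysis should show how much this matters. The planned one disregards NACT when it censors and dates events. But protocol scans stop at NACT, so little can change except that a later death becomes the event. No column asks what happens if NACT or clinical progression is itself the event.

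**Working it through.** **The plan's own figure.** The documents give no design figure for PFS or DoR. The only one is about 90% power for ORR with 55 patients. It reproduces (18 or more responses of 55, exact power 0.893) and is unaffected by this point.

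**Inputs (all assumed, since the documents give none for PFS).** Median time to progression 6 months; median survival after progression 5 months; 10%, 20% or 30% of progressions clinical and not imaged; half of those patients start NACT. The scan schedule is the protocol's: weeks 6, 12, 18, 24, 32, 40, 48, then every 12 weeks from week 60, each within 2 weeks.

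**Hand bound.** With a constant hazard and a 6-month median, true 6-month PFS is 0.5. If a share f of progressions is censored, Kaplan-Meier tends to 0.5^(1−f).
- f = 0.10: 0.536, excess 3.6 points
- f = 0.20: 0.574, excess 7.4 points
- f = 0.30: 0.616, excess 11.6 points

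If EOT scans document half of these progressions, f halves: 0.518, 0.536 and 0.555, excess 1.8, 3.6 and 5.5 points.

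**Simulation with the Table 1 rules.** The gaps come out smaller than the bound, because some patients die without NACT before missing two scans and remain events. The comparator counts clinical progression as the event on its date.

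| Clinical share | 6-month PFS, primary | Comparator | Gap | Median, primary / sensitivity / comparator (months) |
|---|---|---|---|---|
| 10% | 55% | about 52% | 3 points | 7.4 / 7.4 / 7.1 |
| 20% | 58% | about 52% | 6 points | 7.7 / 7.8 / 7.0 |
| 30% | 61% | about 52% | 9 points | 8.9 / 8.8 / 6.9 |

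These figures assume that no EOT scan documents the progression. If half do, the 6-month gap is about 1.5 to 4.5 points and the primary medians are about 7.3, 7.4 and 7.5 months against 7.1, 7.0 and 6.8. Medians jump between scan dates, so the 6-month rate is the steadier measure.

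**Other assumptions.** With median time to progression 3, 5 or 8 months, 70% starting NACT, post-progression survival 6 months and a 24-month cut-off, the gap is about 3 to 11 points, or about 1.4 to 5 if EOT scans document half. The sensitivity estimate differs from the primary by only −0.6 to +3.4 points. For a 5-month median and 20% clinical, 6-month PFS is 52.6% primary, 53.2% sensitivity and 45.7% comparator.

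**Table 1 precedence.** Take a patient whose EOT scan at week 18 shows no progression, who progresses clinically at week 20, takes no NACT and dies at week 36. The scans at weeks 24 and 32 were not done. The row for progression or death without NACT gives an event at week 36. The row for two or more missed scans censors at week 18. If scans no longer required after clinical progression are not missed, only the first row applies. The SAP settles neither question.

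**DoR.** The protocol ends the response at NACT; the SAP censors at the last scan before it. SAP 8 does not list the difference, and SAP 6.3.2 provides alternative censoring for PFS only.

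**The case against.** A reader might infer that the sensitivity analysis cannot reveal the bias at all, or that every deteriorating patient is censored at a last good scan. The documents support neither reading.

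- **The EOT scan comes first.** It is mandatory and precedes NACT. If it shows progression, the primary rule counts an event. This stands, and it roughly halves the effect if half of these progressions are documented. It does not remove the effect: clinical deterioration need not meet RECIST, and a scan can be missed.
- **The sensitivity column does count later progression and death.** Survival is followed every 3 months (Protocol 5.4, 6.6). When death follows soon, the columns separate: with a 5-month median time to progression, 3-month post-progression survival, 20% clinical and all starting NACT, medians are 7.4 primary, 6.6 sensitivity and 5.5 comparator. So the check is weak and late for PFS, not absent. For DoR there is none.
- **Deaths without NACT are not always censored.** How often they follow two missed scans depends on assumed survival: about 67% at 5 months, 53% at 3 and 38% at 2, and only if scans no longer required count as missed.
- **Scope.** The stop at clinical progression concerns patients already off treatment for other reasons, and Protocol 7.7 does not mention it.
- **Precision.** At 55 patients, a 52% rate has a 95% half-width of 1.96 × √(0.52 × 0.48 / 55), about 13 points, wider than the simulated gaps; enrollment ended early. This limits the stakes, but an interval does not correct a shift in one direction.
- **Feasibility.** SAP 6.2.9 records regimen start dates for subsequent therapy. No document shows a dated field for clinical progression.

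**Conclusion.** The point holds in limited form. Censoring at NACT is probably informative and biases descriptive PFS and DoR upward. Under the stated assumptions, 6-month PFS is about 3 to 9 points too high without EOT documentation and about 1.5 to 4.5 points too high if EOT scans document half of the clinical progressions. The direction is more secure than the size, because every input is assumed. Agreement between the two planned PFS columns would be weak evidence of robustness.

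The DoR discrepancy needs no assumptions: the protocol and SAP treat NACT differently, the change is not declared, and no alternative analysis is planned. The Table 1 overlap is likewise a plain ambiguity that two programmers could resolve differently.

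PFS and DoR are secondary endpoints with no test or threshold, so neither the ORR analysis nor the sample size is affected. This is a cheap improvement, not a flaw that undermines the trial.

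**What to change.** 1. Add a PFS sensitivity column to SAP Table 1 that counts the start of NACT as an event on its start date, and clinical progression too where the CRF records a date. Report it beside the primary analysis. Protocol 10.5.2 already allows further PFS analyses with other censoring rules.
2. Reconcile DoR in SAP 5.2.1 with Protocol 10.5.2. If the SAP keeps its censoring rule, list the difference in SAP 8.
3. State which Table 1 row applies to a death without NACT after two or more missed scans, and whether scans no longer required count as missed.

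The cost is SAP wording and one more Kaplan-Meier run; start dates of subsequent therapy are already collected. The downside is that the new column is somewhat pessimistic, since some patients change therapy for intolerance rather than progression. A column built on NACT dates alone would also recover only part of the simulated gap, because the comparator above counts every clinical progression.

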5.2.3. Overall Survival (OS)

Overall survival is defined as the time from the date of seribantumab treatment initiation (Dose 1) to the date of death from any cause.

OS in days will be calculated as:

• OS (days) = Date of death – first dose date + 1

OS in months will be calculated as:

• OS (months) = 12*OS (days)/365.25

Patients who are alive at the time of database lock or lost to follow-up will be censored on the date the patient was last known to be alive based on data collected in the database.

5.2.4. Clinical Benefit Rate (CBR)

Clinical benefit rate is defined as the proportion of patients who achieve PR, CR, or SD which is maintained through at least 24 weeks per RECIST v1.1. Tumor assessments after the initiation of new anticancer therapy should not be used to derive the CBR.

Patients with no evaluable post-baseline disease assessments (i.e., NE) or with ongoing SD but short of 24 weeks at the time of analysis will be considered as not having attained clinical benefit and included in the denominator in the calculation of the CBR.

5.3. Safety Endpoints

5.3.1. Treatment-emergent Adverse Events (TEAEs)

Adverse events (AE) will be coded using the Medical Dictionary for Regulatory Activities (MedDRA) dictionary v26.0 or later. Severity will be graded according to the National Cancer Institute (NCI) Common Terminology Criteria for Adverse Events (CTCAE) v5.0. All AEs, complaints, or symptoms that occur from the time that written informed consent has been obtained through the EOT visit are to be recorded on the appropriate case report form (CRF).

TEAEs are defined as any event that occurred after the first dose of study drug and 28 days after the last dose of seribantumab that was not present prior to study drug administration or worsened in severity after study drug administration. TEAEs will be summarized in the safety analysis.

5.3.2. Dose Limiting Toxicities (DLTs)

Patients will be monitored during weekly dosing for a period of 28 days (i.e., throughout C1W1, C1W2, C1W3, and C1W4) for the occurrence of dose limiting toxicities (DLTs). Any Grade 3 or 4 hematologic or non-hematologic toxicity considered related to seribantumab will be considered dose limiting. A DLT is defined as any AE meeting specific criteria, occurring during weekly treatment with seribantumab, where the relationship to seribantumab cannot be ruled out. The full list of criteria for determination of DLTs is given in Section 5.2.4.1 of Clinical Protocol Version 7.0.

Any toxicity, regardless of CTCAE grade, resulting in discontinuation or dose reduction of seribantumab treatment during the 28-day DLT evaluation period, except for symptoms related to PD, will be considered a DLT.

5.3.3. Exposure to Study Drug

Seribantumab dosing will consist of weekly dosing until study treatment discontinuation criteria are met.

Total treatment duration:

- Total treatment duration (days) = date of last dose date of first dose + 1
- Total treatment duration (months) = 12*Total treatment duration (days)/365.25

Actual numbers of completed seribantumab infusions:

• Actual numbers completed = actual numbers of completed seribantumab infusions from the first dose to last dose

Actual dose of administered seribantumab infusions (mg):

• Actual dose administered (mg) = actual cumulative dose of administered seribantumab up to the date of last dose

Relative dose intensity (RDI) is the percentage of actual dose administered relative to the intended dose planned through to treatment discontinuation.

RDI will be calculated as follows:

• RDI = 100% * d/D

where d (mg) is actual total dose administered and D (mg) is cumulative dose planned. D is the total dose that would be administered if there were no modification to dose or schedule.

5.4. Pharmacokinetics

The PK of seribantumab will be assessed from plasma samples taken at time indicated in the Schedule of Assessments.

6. STATISTICAL ANALYSES

This section describes the statistical analyses to be conducted in relation to the primary, secondary, and exploratory objectives of the study.

6.1. General Statistical Considerations

In general, analyses specified will follow the multi-cohort nature of the study design. Specifically, analysis of safety (Section 6.4) will be presented by cohort (cohort 1 primary efficacy analysis population, cohort 1, cohort 2, cohort 3) and all cohorts combined based on the safety analysis population. Analysis of patient population (Section 6.2) will be summarized similarly, except for Patient Disposition, which will be summarized for all patients who have signed the informed consent regardless of seribantumab treatment. The efficacy analysis (Section 6.3) primary focus will be on the cohort 1 primary efficacy analysis population patients. Safety and efficacy analysis will also be performed for nonsmall cell lung cancer (NSCLC) vs other tumors within cohort 1 primary efficacy analysis population.

For continuous variables, the number of observations (n), mean, standard deviation, median, minimum, and maximum will be provided as summary statistics. The mean and median will be reported to one additional decimal place compared to the original data. The standard deviation will be reported to two additional decimal places compared to the original data and the minimum and maximum will be reported to the same number of decimal places as the original data.

For categorical variables, the frequency and percentage in each category will be displayed. Percentages (e.g., for AEs and concomitant medications) will be calculated out of the population total for each cohort. Footnotes will clarify the denominator used in each output if other than the analysis set stated in the title. Percentages will be reported to one decimal place throughout unless the percentage is 100 (in which case no decimal places will be presented) or if the frequency count is zero (in which case no percentage will be presented).

For time to event data, unless otherwise noted, the median value, 25th percentile and 75th percentile will be calculated using the Kaplan-Meier method. In addition, the minimum and maximum values of the time to event data will be calculated with an indication of whether that value is an event or censored. However, if both an event and a censored observation contributes to the minimum or maximum then in the case of the minimum the value would be indicated as an event and in the case of a maximum the value would be indicated as censored. Furthermore, the Brookmeyer and Crowley method will be used to calculate the CI of the median value estimated using the Kaplan-Meier method (Brookmeyer and Crowley 1982). Also, the Greenwood formula will be used to calculate the CI of the survival rate (or the rate of interest pertaining to the time to event data), at a given time point estimated using the Kaplan-Meier method for the time to event data (Kalbfleisch and Prentice 2002).

6.1.1. Baseline Definition

Unless stated otherwise, the baseline value is defined as the last non-missing measurement prior to the first administration of seribantumab. Study Day 1 will be considered as the date

of the first dose of seribantumab. The change from baseline for a parameter is calculated as (observed value at visit - baseline value).

6.1.2. Multiple Comparisons

No multiple comparisons adjustment will be applied to the efficacy analysis.

6.1.3. Handling of Dropouts or Missing Data

Unrecorded data values will be recorded as missing. Only recorded (i.e., complete) data values will be used for statistical analyses. In general, invalid or missing values will not be imputed unless stated otherwise.

In cases of missing or incomplete dates (e.g., AEs and concomitant medications), the missing component(s) will be assumed as the most conservative value possible. For example, AEs with missing start dates, but with stop dates either overlapping into the treatment period or missing, will be counted as treatment-emergent, taking the worst-case approach. When partial dates are present in the data, both a partial start date and/or a partial stop date will be evaluated to determine whether it can be conclusively established that the AE started prior to the start of study drug or ended prior to the start of study drug. If the above cannot be conclusively established based on the partial and/or present dates, then the AE will be considered as treatment-emergent. Actual data values as they appear in the original CRFs will be presented in the data listings.

To be conservative in the case of missing causality assessment for AEs after data querying, AEs will be assumed to be related to study drug. If the CTCAE grade is missing after data querying it will not be imputed and the patient will be presented in table summaries based on the maximum CTCAE grade of all other recorded AEs meeting applicable criteria.

